6.1.6 Interim Analyses and Data Monitoring

As stated in the protocol, if determined appropriate by the Sponsor, limited safety and efficacy interim analysis on tumor shrinkage and biomarkers may be performed.

Once biomarker results are available for subjects in Cohorts 1 and 2, and again after Cohort 3 subjects have biomarker results, the database will be used to report on limited safety and efficacy results. The sponsor and the CRO (QST) will be unblinded at this time. Site staff will remain blinded.

6.1.7 Multicenter Studies

The study will be conducted at one metasite in the United States with the intention of pooling the results for analysis.

6.1.8 Multiple Comparisons/Multiplicity

Not applicable. Inferential tests will not be performed.

6.1.9 Use of an Efficacy Subset of Subjects

A Per Protocol population is defined below.

6.1.10 Active-Control Studies Intended to Show Equivalence

Not applicable to this study.

6.1.11 Examination of Subgroups

Not applicable to this study.

6.2 Disposition of Subjects

The number of subjects included in each analysis population (ITT, Safety, and Per Protocol) will be summarized by treatment group. The number of subjects randomized, completed, and discontinued (including the reasons for discontinuation) will be summarized for each treatment group.

Reasons for exclusion from study populations will be included in a by-subject listing.

6.3 Protocol Deviations

All protocol deviations will be reported to PellePharm and recorded throughout the study. A listing of protocol deviations by treatment by subject will be included in the final study report.

6.4 Data Sets Analyzed

6.4.1 Intent-to-Treat (ITT) Population

All subjects who are randomized and dispensed study drug will be included in the ITT analysis set. Subjects will be analyzed according to the treatment group they were randomized. All efficacy analyses will be presented using the ITT population and the Per Protocol population.

6.4.2 Safety Population

All subjects who are randomized, receive at least 1 confirmed dose of study drug and have at least one post-baseline safety assessment will be included in the safety analysis set. All safety analyses will be according to the treatment actually received.

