- To evaluate the utility of an investigator static global tumor assessment (ISGTA) in assessing the proportion of baseline treatment-targeted BCCs that are evaluated as being clear or almost clear.
- Histologic Cure: The proportion of the excisional samples obtained at or shortly after the Week 12 visit that demonstrate no residual BCC.

Statistical Methods:

All subjects who are randomized and dispensed study drug will be included in the intent-to-treat (ITT) analysis set. All subjects who are randomized, receive at least one confirmed dose of study drug, and have at least one post-baseline safety assessment will be included in the safety population.

No imputation will be made for the primary endpoint. For the secondary endpoint, last observation carried forward (LOCF) will be used to impute efficacy data that are missing post-baseline through Week 12. No imputations will be made for missing safety data.

Per protocol analysis will be performed – we will exclude samples with insufficient BCC, subjects with poor treatment compliance, or tumors where the diameter was incorrectly measured based on review of photographs. We will also analyze BCC size change based on photographs.

Efficacy Summaries:

The efficacy endpoints are intended to compare once and twice daily application of 2% patidegib gel, 4% patidegib gel, and vehicle gel. Efficacy assessments will be summarized descriptively by treatment group and visit.

Primary Efficacy Endpoints:

• Change in GLI1 mRNA levels in drug-treated vs. vehicle-treated tumors after 12 weeks of treatment.

Secondary Efficacy Endpoint:

• Decrease in tumor size defined as percent decrease in the greatest diameter of baseline treatment-targeted BCCs at the Week 12.

Exploratory Efficacy Endpoint:

- The proportion of baseline treated tumors are smaller based on photographic review
- The proportion of baseline treatment targeted BCCs that are evaluated as being clear or almost clear at Baseline, Weeks 2, 6, 8, 10, and 12 based on the ISGTA.

Efficacy Analyses:

The primary endpoint and the secondary endpoints of change in tumor size, and reduction in the HH signaling pathway will be evaluated with an analysis of covariance (ANCOVA) with treatment group as factor and baseline value as a covariate. Pairwise comparisons will be performed using contrasts within the ANCOVA. Additionally, t-tests for pairwise comparisons of the primary endpoint will be done, or alternatively a non-parametric approach may be used.

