5.1 Overall Study Design and Plan

This is a double-blind, dose escalating, randomized, vehicle-controlled study designed to assess the efficacy and safety of patidegib gel 2% and 4% in comparison with vehicle applied once or twice daily. The population of subjects will be enrolled from the PPD.

Approximately 36 subjects who meet the study entry criteria will be randomized to one of four sequential cohorts. Each cohort will have 6 subjects randomized to active drug and 3 randomized to vehicle. The four sequential cohorts will be patidegib gel 2% or vehicle applied once daily, patidegib gel 4% or vehicle applied once daily, patidegib gel 2% or vehicle applied twice daily, and patidegib gel 4% or vehicle applied twice daily. As soon as one cohort has been enrolled the next cohort will be recruited. The study drug will be applied topically to the treatment-targeted

nodular BCCs once or twice daily for 12 weeks of treatment. Subjects will apply their treatments at home as explained by the Investigator or their designee. The subject will apply the initial application under the supervision of the study staff. If a subject has a treatment targeted BCC on an anatomical location that the subject cannot reach such as the back, a friend or family member may apply the treatment. In this case the friend or family member applying the gel, a woman of childbearing potential should follow the birth control requirements outlined in the Inclusion Criteria, and the person should apply the gel using a latex or vinyl glove. As skin cancer patients are routinely advised, all subjects will be instructed to avoid exposure to direct sunlight and to continue their use of sunscreens to minimize their exposure to ultraviolet (UV) radiation.

It should be noted that 3 months of treatment with oral vismodegib caused a 50% reduction in the sum of the greatest diameters of BCCs in 50% of BCNS patients. Therefore, even if topical patidegib were as effective as oral vismodegib in shrinking BCCs there likely will be enough residual BCC at Week 12 to allow for meaningful evaluation of biomarkers.

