9.1.2 Baseline Visit (Day 1)

The following procedures will be conducted at this visit:

- 1. Record any changes in medical history since Screening.
- 2. Record changes in any previous BCC medications since the previous visit in eCRF. Check for prohibited concomitant therapies and confirm any therapy that requires a washout prior to Baseline as per Section 7.4.
- 3. Record changes in any concomitant medications since the previous visit in eCRF. Check for prior and concomitant therapies as per Section 7.4.

- 4. Verify that the subject continues to meet the applicable study eligibility criteria as outlined in Sections 6.1 and 6.2.
- 5. An abbreviated physical examination including measurements of weight.
- 6. The Investigator will perform the clinical evaluation to identify the treatment-targeted tumors which will be clinically classified as superficial, nodular, infiltrative, morphic, pigmented or micronodular/morpheaform to be circled in ink, photographed, measured, and recorded on a body diagram.
- 7. The Investigator or designee will assess the areas to be treated by observations and questioning the subjects as necessary for the signs and symptoms of irritation including pain/burning, pruritus, erythema, edema, and scabbing/crusting.
- 8. The Investigator will query the subject about the symptoms of any abnormalities in taste, frequency and severity of muscle cramps, recent changes in quality or quantity of hair in treated and untreated areas and any change in frequency of shaving of treated or untreated areas, any change in frequency of obtaining haircuts.
- 9. Randomize the subject to a treatment group and record the assigned kit number in the source document and in the eCRF.
- 10. The designated study drug staff will weigh each tube within the assigned kit and dispense them to the subject.
- 11. The Study Coordinator or designee will instruct the subject on the proper application procedure for the study drug. For the first application, the subject will apply the study drug at the investigational center under the direction of the Study Coordinator or designee. The study drug should be applied after all clinical assessments. The subjects will be asked to avoid exposure to direct sunlight on the initial application day and thereafter. The Study Coordinator or designee will instruct the subjects to apply the study drug once or twice daily at home and review patient instruction sheets and dosing card.

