- 12. Record any AEs reported spontaneously by the subject.
- 13. If the subject is a woman of childbearing potential, the Study Coordinator or designee will provide the subject with three home pregnancy urine tests.
- 14. Schedule the next study visit at Week 2 (Day 15 ± 2 days).

9.1.3 Weeks 2, 6, 8, and 10

The following procedures will be conducted at this visit:

- 1. Record changes in any concomitant medications since the previous visit in the eCRF. Check for prior and concomitant therapies as per Section 7.4.
- 2. Record any new AEs reported spontaneously by the subject or changes in any ongoing AEs.
- 3. The treatment-targeted BCCs identified by the Investigator at the Baseline visit will be photographed and measured using the provided hand held device. *For the Week 6 visit*

- *only*, the treatment-targeted tumors will be, circled in ink, photographed, measured, and recorded on a body diagram.
- 4. The Investigator or designee will assess the treated areas by observations and questioning the subjects as necessary for the signs and symptoms of irritation including pain/burning, pruritus, erythema, edema, and scabbing/crusting.
- 5. The Investigator will question the subject about any concurrent illness or systemic sign or symptom including but not limited to fatigue, loss or change in taste, nausea, vomiting, diarrhea, muscle spasms or cramps, changes in quality or quantity of hair in treated areas and any change in frequency of shaving or haircuts.
- 6. Collect blood samples for routine laboratory analysis (CBC/Diff and serum chemistry) (*Weeks 6 only*).
- 7. If the subject is a woman of childbearing potential, they will take a home pregnancy urine test and disclose the results to the Investigator or designee (*Weeks 2, 8, and 10 only*).
- 8. The Study Coordinator or designee will weigh the previously dispensed study drug tube. The study coordinator or designee will weigh and dispense a new study drug tube from the subject assigned kit if necessary. (*Baseline and Week 6 only*)
- 9. Any missed doses or deviations should be reported.
- 10. The Study Coordinator or designee will remind the subject of the proper technique for application of the study drug. If needed, the subject can apply the study drug at the investigational center during the day under the direction of the Study Coordinator or designee to confirm proper technique.
- 11. Schedule the next study visit.

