10.1 Analysis Populations

Per protocol analysis will be performed —samples with insufficient BCC, subjects with poor treatment compliance, or tumors where the diameter was incorrectly measured based on review of photographs will be excluded. BCC size change based on photographs will also be analyzed. Safety analyses will be performed using the safety population. All subjects who are randomized, receive at least 1 confirmed dose of study drug and have at least one post-baseline safety assessment will be included in the safety analysis set.

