3. STUDY OBJECTIVES

The primary objectives of the study are to evaluate the following:

- 1. The safety and tolerability of treatment with patidegib gel 2% or 4% or vehicle applied once or twice daily for 12 weeks.
- 2. The molecular efficacy of treatment as defined by reduction in the hedgehog (HH) signaling pathway after treatment with patidegib gel 2% or 4% or vehicle applied twice daily for 12 weeks to treatment-targeted BCCs.

The secondary objective of the study is to evaluate the following:

1. The clinical efficacy of patidegib as defined by the percent decrease in greatest diameter of baseline treatment targeted basal cell carcinomas after 12 weeks of treatment. Treatment targeted BCCs will be biopsied prior to treatment to confirm the clinical diagnosis of nodular BCC. Eligible tumors will have the clinical features of nodular BCC and prior to biopsy will be no less than 5 mm or greater than 20 mm in longest diameter on the face (excluding the nose and periorbital skin) and no less than 9 mm or greater than 20 mm in longest diameter at sites other than the face.

Exploratory objectives:

- 1. To evaluate the utility of an investigator static global tumor assessment (ISGTA) in assessing the proportion of baseline treatment-targeted BCCs that are evaluated as being clear or almost clear.
- 2. To evaluate the utility of blinded assessment of change in BCC size using photographs.

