6.4.3 Per Protocol (PP) Population

All subjects in the ITT population who complete the Week 12 evaluation without any significant protocol violations will be included in the PP population and analyzed according to the treatment group they received. The PP population will include subjects in the safety population who do not meet any of the following criteria:

- Violated the inclusion/exclusion criteria;
- Have taken any interfering concomitant medication;
- Did not attend the Week 12 visit;
- Have not been compliant with the dosing regimen, between 80% to 120%
- Had samples with insufficient BCC
- Had tumors where the diameter was incorrectly measured based on review of photographs

Subjects that discontinue from the study due to an adverse event related to study treatment or documented lack of treatment effect will be included in the PP population. Prior to breaking the blind, other additional criteria may be added to the list to accommodate for unforeseen events that occurred during the conduct of the trial that result in noteworthy study protocol violations.

Efficacy analyses performed on a by-tumor basis will include tumors from subjects who are not excluded for any of the above reasons.

All efficacy analyses will be performed on the ITT population as well as on the PP population.

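### The safety population omits dosed subjects with no post-baseline safety assessment, so a one-dose exit, and possibly a Day 1 event, can be missing from the exposure, AE and tolerability tables

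*SAP*

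**What the plan says.** SAP 6.4.2 admits to the safety population randomized subjects who "receive at least 1 confirmed dose of study drug and have at least one post-baseline safety assessment", and analyzes them by the treatment they actually received. The protocol synopsis has the same rule (subjects who "receive at least one confirmed dose of study drug, and have at least one post-baseline safety assessment will be included in the safety population"), and so does protocol 10.1, which adds: "Safety analyses will be performed using the safety population". The SAP shells for exposure, dermal tolerability, systemic symptoms, AEs, laboratory results and vital signs are all labelled for this population.

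Safety is the first primary objective in SAP section 3: "The safety and tolerability of treatment with patidegib gel 2% or 4% or vehicle applied once or twice daily for 12 weeks".

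On dosing, protocol 5.1 states: "The subject will apply the initial application under the supervision of the study staff". Protocol 9.1.2 places this at the Baseline visit, where "the subject will apply the study drug at the investigational center under the direction of the Study Coordinator or designee", after the clinical assessments are finished. The remaining Baseline steps record any AE the subject volunteers and end with the instruction "Schedule the next study visit at Week 2" (Day 15 ± 2).

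SAP 6.8.2 counts an AE as treatment-emergent if it begins on or after the date of first application. Neither document defines a post-baseline safety assessment.

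**The concern.** Because the first dose is taken under supervision, a confirmed dose should be on record for nearly every randomized subject. The condition that does the excluding is therefore the second one, and it depends on something that happens after exposure: whether the subject is assessed again. A subject who applies the gel once and does not come back is exposed but leaves the denominators of the tables serving a primary objective. Poor tolerability is one possible reason for not coming back, so the selection may not be neutral.

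There is also a gap between two definitions. An event that arises on Day 1 after the application is treatment-emergent, yet the subject who had it may not belong to the population on which TEAEs are tabulated. Whether a volunteered Day 1 report counts as a post-baseline safety assessment is left open. Sponsor and CRO are to be unblinded after Cohorts 1 and 2 and again after Cohort 3 (SAP 4.1.3 and 6.1.6), so a case-by-case decision could be made with treatment known.

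**Working it through.** **1. Planned denominators.** Protocol 5.1 gives four cohorts of 6 active and 3 vehicle: 4 × (6 + 3) = 36, which reproduces the planned enrollment. SAP 6.1 pools vehicle: 4 × 3 = 12. The safety columns are therefore 6, 6, 6, 6 and 12. Subjects who discontinue are not replaced. One exclusion removes 1/6 = 16.7% of an active column or 1/12 = 8.3% of the vehicle column.

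**2. Whom the clause removes.** Take a subject who is randomized, doses once under supervision and has no later contact.
- Randomized: yes. Confirmed dose: yes (protocol 5.1 and 9.1.2).
- Post-baseline safety assessment: none scheduled before Week 2, so no.
- Result: outside the safety set, but inside ITT, which needs only randomization and dispensing (SAP 6.4.1).

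**3. Where the subject is still shown.** Table 14.1.1 is headed for all subjects and gives, by arm, discontinuation reasons and the number excluded from the safety population. Listing 16.2.3 gives the reasons for exclusion. SAP 6.8.2 plans a listing of all AEs and states no restriction to the safety set.

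**4. Effect on a rate in a 6-subject arm when one such subject is removed** (exact Clopper-Pearson 95% limits in parentheses):

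| Case | Current definition | All dosed subjects |
|---|---|---|
| Removed subject had the only event | 0/5 = 0% (0% to 52.2%) | 1/6 = 16.7% (0.4% to 64.1%) |
| Another subject had the only event | 1/5 = 20.0% (0.5% to 71.6%) | 1/6 = 16.7% (0.4% to 64.1%) |
| No event in the arm | 0/5 = 0% (0% to 52.2%) | 0/6 = 0% (0% to 45.9%) |

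The direction depends on the case: the event is lost in the first row, and the reported rate rises in the second.

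**5. How often.** The documents give no early-loss rate. If d is the assumed proportion who dose once and have no later assessment, the chance of at least one among n subjects is 1 − (1 − d)^n:

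| Assumed d | At least one of 36 | At least one in a given 6-subject arm | Expected of 36 |
|---|---|---|---|
| 1% | 30.4% | 5.9% | 0.4 |
| 3% | 66.6% | 16.7% | 1.1 |
| 5% | 84.2% | 26.5% | 1.8 |
| 10% | 97.7% | 46.9% | 3.6 |

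These rows illustrate a range of assumptions and are not estimates for this trial.

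**The case against.** The case for leaving the text alone is fairly strong. Protocol and SAP agree, so there is no inconsistency between them. The analysis is descriptive, so no test is affected. The group clearly excluded is narrow: early leavers are asked to complete the Week 12 assessments, loss to follow-up must be documented with calls and a certified letter (protocol 6.3), and Week 2 may be done by telemedicine, so a subject who reports intolerance by one of these routes would arguably qualify. The 0/5 case needs a recorded Day 1 event that nobody counts as an assessment. Keeping a subject with no safety information in the denominator also has a price, because unknown status is then treated as event-free. All of this stands, and it limits the size of the point.

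Three stronger readings are tempting, and the documents do not support them.
- A reader might infer that early exits are hidden and discontinuation rates distorted. Table 14.1.1 covers all subjects and shows both by arm. Only the row for stopping study medication because of an AE, in Table 14.3.2.1.1, is computed on the safety set.
- A reader might infer from "The PP population will include subjects in the safety population" (SAP 6.4.3) that the condition damages the per-protocol analysis. That set already excludes anyone who did not attend Week 12. The exception for discontinuation due to a related AE or documented lack of effect would normally rest on post-dose information.
- A reader might take the move from 1/6 to 1/5 as a hidden event. It raises the reported rate, and it arises when the removed subject had no event.

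The objection does not remove the dependence on a post-dose condition in tables serving a primary objective, or the missing definition that leaves a Day 1 TEAE without a sure place in them.

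**Conclusion.** The point holds in a limited form. The definition mainly removes exposed subjects who left early, and only from summaries run on the safety population. One removal takes 16.7% of an active column. In the worst case, where that subject had the arm's only event, 1/6 (16.7%) is reported as 0/5 (0%); where another subject had it, 1/6 is reported as 1/5 (20.0%). The worst case assumes that a Day 1 report is not accepted as a post-baseline safety assessment, which the documents neither confirm nor exclude. How often any of this would happen is unknown. It is a minor, optional improvement and does not put the trial's conclusions in doubt.

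**What to change.** In SAP 6.4.2, the protocol synopsis and protocol 10.1, define the safety population as all randomized subjects who receive at least one confirmed dose, and keep analysis by treatment actually received. Report for each group the number with no post-baseline safety assessment; Listing 16.2.3 can carry the same flag by subject.

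The cost is one deleted clause in each place and one added count. No new data or imputation is needed, since the by-visit shells already show their own number of subjects or tumors. SAP 6.1.3 still keeps early-termination and unscheduled data before Day 13 out of the analyses, so the gain lies in the exposure and AE tables. The drawback is that subjects whose later status is unknown stay in the denominator as event-free and may slightly lower AE rates; the reported count lets the reader see by how many.

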6.4.3 Per Protocol (PP) Population

All subjects in the ITT population who complete the Week 12 evaluation without any significant protocol violations will be included in the PP population and analyzed according to the treatment group they received. The PP population will include subjects in the safety population who do not meet any of the following criteria:

- Violated the inclusion/exclusion criteria;
- Have taken any interfering concomitant medication;
- Did not attend the Week 12 visit;
- Have not been compliant with the dosing regimen, between 80% to 120%
- Had samples with insufficient BCC
- Had tumors where the diameter was incorrectly measured based on review of photographs

Subjects that discontinue from the study due to an adverse event related to study treatment or documented lack of treatment effect will be included in the PP population. Prior to breaking the blind, other additional criteria may be added to the list to accommodate for unforeseen events that occurred during the conduct of the trial that result in noteworthy study protocol violations.

Efficacy analyses performed on a by-tumor basis will include tumors from subjects who are not excluded for any of the above reasons.

All efficacy analyses will be performed on the ITT population as well as on the PP population.

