Subjects will return their tubes of study drug, which will be evaluated for drug usage compliance. While individual usage rates of topical products will vary, the use of a dosing card should help limit the variation in dosing inherent with topical products. Approximately 20 mg of the gel represents a single applied dose. Thus a subject treating a single tumor once daily for 12 weeks will apply a total dose of 1.6 gm of gel and those treating two tumors twice daily for 12 weeks will apply a total dose of 6.4 gm of gel. In terms of actual drug, 20 mg of patidegib gel 2% and 4% contains 0.4 mg and 0.8 mg of patidegib, respectively. Thus the total dose of drug in the 2% once daily group treating a single tumor will be approximately 34 mg while subjects treating two tumors twice daily for 12 weeks with patidegib gel 4% will receive a total of 134 mg of patidegib. To put this in perspective in previous trials with an oral formulation of patidegib subjects were treated with a daily oral dose of 130 – 160 mg, many for longer than 6 months.

Upon completion of the 12-week treatment period, all subjects will be asked to return to the investigational center for final evaluation. At the Week 12 visit the treatment site(s) will be excised. The area excised should at a minimum include the original diameter of the tumor. This means that if the tumor has shrunk in size the entire original area of the BCC will be excised, not just the visually apparent residual tumor. During the study, subjects will be allowed to use moisturizers and emollients and sunscreen. The Investigator will assess the areas affected at each visit.

The treatment-targeted BCC(s) will be identified by the Investigator at the Baseline visit and will be circled in ink at Baseline, Weeks 6 and 12, and photographed, and measured at all study visits (Baseline, Weeks 2, 6, 8, 10, and 12).

Biomarkers: On each subject one or two baseline previously untreated nodular BCCs designated as a treatment-targeted tumor will be biopsied and at the end of 12 weeks of treatment the treatment

PellePharm, Inc.

Dose Escalating Study in Sporadic Basal Cell Carcinomas

site(s) will be excised. Both samples will be evaluated histologically and for determination of GLI1 mRNA levels.

Blood samples for complete blood count and serum chemistry and urine for urinalysis will be collected from subjects at Screening, Week 6, and Week 12.

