6.4 Study Drug Discontinuation

The Investigator may discontinue study drug administration for any subject at any time. The study drug administration must be discontinued for any of the following:

- Occurrence of an exclusion criterion that is clinically relevant and affects the subject's safety, if discontinuation is considered necessary by the Investigator.
- Occurrence of AEs, if discontinuation of study drug is desired or considered necessary by the Investigator or subject.
- Pregnancy
- Disease progression -The Investigator and/or PSCP believe that delaying the treatment of the treatment targeted tumor until the end of the trial would cause harm to the subject.

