6.8 Safety Evaluation

6.8.1 Extent of Exposure and Compliance

The extent of exposure to study drug in each treatment group will be summarized by days with applications, total number of applications, and number of missed applications. This data will also be provided in a listing.

Percent compliance will be calculated for each subject as follows:

(a) Expected Number of Applications = (Date of Last Application – Date of First Application + 1) * Number of Expected Applications per day, accounting for possible single applications on First and/or Last Day

(b) Total Number of Applications = Expected Number of Applications – Total Number of Missed Applications

Compliance = (b) / (a) * 100

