Smaller	xx (xx.x%)	xx (xx.x%)	xx (xx.x%)	xx (xx.x%)	xx (xx.x%)
Not smaller	xx (xx.x%)	xx (xx.x%)	xx (xx.x%)	xx (xx.x%)	xx (xx.x%)
P-value versus Vehicle Gel ^b	x.xxx	X.XXX	x.xxx	x.xxx	
P-value versus Patidegib Gel 2% QD ^b		X.XXX	X.XXX	X.XXX	
P-value versus Patidegib Gel 2% BID ^b			X.XXX	X.XXX	
P-value versus Patidegib Gel 4% QD ^b				X.XXX	
P-value All Patidegib vs Vehicle Gel ^b					X.XXX

P-value versus Vehicle Gel ^c	X.XXX	X.XXX	X.XXX	X.XXX
P-value versus Patidegib Gel 2% QD ^c		X.XXX	X.XXX	X.XXX
P-value versus Patidegib Gel 2% BID ^c			X.XXX	X.XXX
P-value versus Patidegib Gel 4% QD ^c				X.XXX
P-value All Patidegib vs Vehicle Gel ^c				

Repeat for Week 12.

SOURCE: USERNAME\SPONSOR\PROJECT\JOBNAME (DATE,TIME)

Table 14.2.4.2: Analysis of the Exploratory Efficacy Endpoint: Area of Baseline Treated Tumors based on Photographic Review (Per Protocol Population) As Table 14.2.4.1 but using Per Protocol population.

Statistical Analysis Plan for PellePharm, Inc. Protocol Number: 926-202

X.XXX

a Defined as demonstrating no residual BCC.
 b P-value of pairwise comparison using ANCOVA with treatment group as a factor and Baseline value as a covariate.
 c P-value from Cochran-Mantel-Haenszel (CMH) test.

Table 14.3.1.1: Summary of Extent of Exposure and Compliance (Safety Population)

	Patidegib Gel 2% QD	Patidegib Gel 2% BID	Patidegib Gel 4% QD	Patidegib Gel 4% BID	Vehicle Gel
	(N=xx)	(N=xx)	(N=xx)	(N=xx)	(N=xx)
Number of Days oaf Exposure					
n	XX	XX	XX	XX	XX
Mean	XX.X	XX.X	XX.X	XX.X	XX.X
SD	XX.XX	XX.XX	XX.XX	xx.xx	XX.XX
Median	XX.X	XX.X	XX.X	XX.X	XX.X
Min. to Max.	xx to xx	xx to xx	xx to xx	xx to xx	xx to xx
Number of Applications ^a					
n	XX	XX	XX	XX	XX
Mean	XX.X	XX.X	XX.X	XX.X	XX.X
SD	XX.XX	XX,XX	XX.XX	XX.XX	XX.XX
Median	XX.X	XX.X	XX.X	XX.X	XX.X
Min. to Max.	xx to xx	xx to xx	xx to xx	xx to xx	xx to xx
Number of Missed Applications					
n	XX	XX	XX	XX	XX
Mean	XX.X	XX.X	XX.X	XX.X	XX.X
SD	xx.xx	XX.XX	XX.XX	XX.XX	XX.XX
Median	XX.X	XX.X	XX.X	XX.X	XX.X
Min. to Max.	xx to xx	xx to xx	xx to xx	xx to xx	xx to xx
Compliance (%)					
N	XX	XX	XX	XX	XX
Mean	XX.X	XX.X	XX.X	XX.X	XX.X
SD	XX.XX	XX.XX	XX.XX	XX.XX	xx.xx
Median	XX.X	XX.X	XX.X	XX.X	XX.X
Min. to Max.	xx to xx	xx to xx	xx to xx	xx to xx	xx to xx

^a The total number of applications was calculated form the first date of treatment and the last date of treatment minus the missed applications.

SOURCE: USERNAME\SPONSOR\PROJECT\JOBNAME (DATE,TIME)

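### The SAP's compliance percentage cannot exceed 100% and stops at the last application, so the Per Protocol 80%–120% band has no working upper limit and can pass a subject who stops gel early.

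*SAP*

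**What the plan says.** SAP 6.4.3 lists the reasons for exclusion from PP. One is that subjects "Have not been compliant with the dosing regimen, between 80% to 120"%. It does not say what the percentage is a percentage of, and it cites no other section. A separate criterion excludes subjects who did not attend Week 12. Subjects who leave the study because of a related adverse event or documented lack of effect are kept.

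SAP 6.8.1 gives the only formula:

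- (a) "Expected Number of Applications = (Date of Last Application – Date of First Application + 1) * Number of Expected Applications per day", with an allowance for single applications on the first or last day
- (b) "Total Number of Applications = Expected Number of Applications – Total Number of Missed Applications"
- "Compliance = (b) / (a) * 100"

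Footnote a of Table 14.3.1.1 repeats the rule: "The total number of applications was calculated form the first date of treatment and the last date of treatment minus the missed applications".

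Protocol 5.1 points to tube weights: "Subjects will return their tubes of study drug, which will be evaluated for drug usage compliance". The SAP lists those weights (Listing 16.2.5.1) but builds no percentage from them. Protocol 10.1 excludes poor compliance from the per-protocol analysis, while protocol 10.5 plans no formal evaluation of compliance. Protocol 6.4 treats stopping drug separately from withdrawal from the study (6.3): "The Investigator may discontinue study drug administration for any subject at any time".

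**The concern.** A PP compliance rule should remove subjects who received clearly too little or too much of the assigned regimen. This one has two faults.

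First, extra applications do not enter the formula, so the upper limit has nothing to act on. The trial compares once-daily with twice-daily use, yet a once-daily subject who applied gel more often than assigned would score no higher than 100%.

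Second, the denominator ends at the subject's own last application. Doses not taken after a permanent stop drop out of the calculation, while the same number missed mid-course counts in full. PP membership then depends on when doses were missed rather than how many, and the subject with less exposure can be the one who is kept.

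**Working it through.** **Inputs.** Treatment is planned for 12 weeks, taken as 84 days (84 applications once daily, 168 twice daily). The Week 12 visit is on Day 85 ± 3 (protocol Table 1), so a course ending the day before the visit lasts 81 to 87 days. Each cohort has 6 active subjects (protocol 5.1). The 80%–120% band is a stated threshold, so there is no derived figure to reproduce; the test is how the formula behaves against it.

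**Upper limit.** With E expected and M missed applications, compliance = (E − M)/E × 100. Since M ≥ 0, the maximum is 100%: 84/84 or 168/168. The first-day and last-day allowance changes numerator and denominator equally (for example 166/166). As an illustration, 126 applications against 84 expected is truly 150%, but the formula returns 100%. The lower limit does act on doses missed between first and last application: up to 16 of 84 or 33 of 168 may be missed.

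**Early stop, no earlier missed dose, later doses not logged as missed.** For a stop after Day s, E = s and M = 0, so the score is s/s = 100%. The share of a planned course of D days is s/D. Application frequency cancels.

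| Stop after Day | SAP score | Share, D = 84 | Share, D = 81 | Share, D = 87 |
|---|---|---|---|---|
| 14 | 100% | 14/84 = 16.7% | 17.3% | 16.1% |
| 42 | 100% | 42/84 = 50.0% | 51.9% | 48.3% |
| 67 | 100% | 67/84 = 79.8% | 82.7% | 77.0% |

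The last stop day below 80% of the course is Day 67 for D = 84, Day 64 for D = 81 and Day 69 for D = 87. Every stop up to that day passes the SAP criterion.

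**Same exposure, opposite result.** Take 67 once-daily applications in an 84-day course. With a 17-day gap mid-course, (84 − 17)/84 = 79.8%, excluded. With a stop after Day 67, 67/67 = 100%, kept.

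**Early stop, later doses logged as missed.** The numerator now loses doses the denominator never contained: (s − (84 − s))/s.

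| Stop after Day | Score |
|---|---|
| 28 | −100% |
| 42 | 0% |
| 56 | 50% |
| 67 | 74.6% |
| 70 | 80% |

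The SAP does not say which of the two readings applies.

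**Who is affected.** Subjects who leave the study before Week 12 have their final evaluations at early termination (protocol 6.3). Most are removed by the attendance criterion, and the rest are kept by design. What remains is subjects who stop gel but stay and attend Week 12.

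**The case against.** The strongest reply is that protocol 7.5 has missed applications documented in the eCRF, and Table 1 has subjects record missed doses. If doses after a stop are logged this way, the score is below 80% for every stop through Day 69, close to the Day 67 cut-off of a planned-course rule, so early stoppers would be excluded after all. That is correct as arithmetic. But protocol 7.5 does not address a permanent stop, and the Table 14.3.1.1 footnote ties the count to the first and last treatment dates. A formula that returns 0% for 42 of 84 applications, and negative values for earlier stops, is not a sound measure even where it happens to exclude the right subject.

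Three further points carry weight:

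- Formal discontinuation mostly leads to an early-termination visit, so the stop-but-stay group is narrow and its size cannot be estimated from the documents.
- A weight-based measure may have been intended in 6.4.3. None is defined, so the statement about the 120% limit applies to the 6.8.1 measure.
- Impact is modest. ITT is reported throughout, p-values are descriptive, and days of exposure and missed applications are tabulated. Efficacy is analysed by tumor, so 1/6 is a share of subjects, not of observations. In the pooled comparisons one subject is 1/12 of vehicle (4 × 3) or 1/24 of all patidegib (4 × 6).

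PP also excludes significant protocol violations, and criteria may be added before the blind is broken. These could catch some cases, but only by judgement. SAP 4.1.3 and 6.1.6 unblind the sponsor and CRO after Cohorts 1 and 2 and again after Cohort 3, so later additions would follow partial unblinding.

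**Conclusion.** The concern holds: the rule is wrong as written, not merely short of detail. On the only compliance measure defined, the 120% limit is inoperative. A subject with 42 of 84 once-daily applications can be kept in PP while one with 67 of 84 is excluded.

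The 100% score assumes no missed dose before the stop and that later doses are not entered as missed. If they are entered, the formula fails in a different way. The percentages assume an 84-day course; over 81 to 87 days the day below which a stop is under 80% of the course moves only between Day 64 and Day 69.

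The effect is confined to the PP analyses, where one such subject is 16.7% of a 6-subject active arm. This should be corrected, but it does not threaten the ITT results.

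**What to change.** **SAP 6.8.1.** Count expected applications from first dose to the planned end of treatment: assigned frequency times planned days, either about 84 or up to the day before the actual Week 12 visit. Choose one and state it. End the count at discontinuation only for subjects whom PP keeps by design. Count every scheduled application not made in that period as missed, including those after a permanent stop. Correct the Table 14.3.1.1 footnote to match.

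**SAP 6.4.3.** Cite this measure by section. Either delete the 120% limit or base it on data that can exceed 100%, such as recorded applications or tube weights. Report weight-based use as a descriptive or sensitivity measure, not as a second automatic exclusion.

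**Protocol.** Reconcile 10.5 with 10.1 and 5.1. Before any weight-based figure is used, also reconcile the gel totals in 5.1. It states that "a subject treating a single tumor once daily for 12 weeks will apply a total dose of 1.6 gm of gel" and gives 6.4 gm for two tumors twice daily, whereas about 20 mg per application gives 20 mg × 84 = 1.68 g and 4 × 1.68 = 6.72 g. This review does not say which figure is right.

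**Cost.** SAP wording and programming, using data already planned for Listings 16.2.5.1 to 16.2.5.3, settled before unblinding. The downside is possibly more PP exclusions in arms of 6; ITT is unchanged.
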